5.2.2. Analysis of secondary efficacy endpoints planned in the protocol

The primary analysis of VE on secondary efficacy endpoints **in infants** will be based on the modified Full Analysis - Efficacy set (modified FAS-E). **The analysis of vaccine efficacy in maternal participants will be based on the Exposed set.**

Secondary Efficacy Endpoints	Statistical Analysis Methods

From birth (Visit 1-NB) to 6 months (Visit 4-NB), occurrences of RSV-associated hospitalizations according to the case definitions.
 
From birth (Visit 1-NB) to 6 months (Visit 4-NB), occurrences of all-cause LRTIs
	
CCI
 

From birth (Visit 1-NB) to 6 months (Visit 4-NB), occurrences of all-cause LRTIs with hospitalization
	

From birth (Visit 1-NB) to 12 months, occurrences of severe medically assessed, RSV-associated LRTIs according to the case definitions
	

From birth (Visit 1-NB) to 12 months, occurrences of any medically assessed, RSV-associated LRTIs according to the case definitions.
	

From birth (Visit 1-NB) to 6 months (Visit 4-NB), occurrences of severe medically assessed, RSV-associated LRTIs according to the case definition, for RSV subtype A and RSV subtype B separately.
	

From birth (Visit 1-NB) to 6 months (Visit 4-NB), occurrences of any medically assessed, RSV-associated LRTIs according to the case definition, for RSV subtype A and RSV subtype B separately.
	

Secondary Efficacy Endpoints	Statistical Analysis Methods
From birth (Visit 1-NB) to 4 months (Visit 3-NB), occurrences of severe medically assessed, RSV-associated LRTIs according to the case definition.	CCI
From birth (Visit 1-NB) to 4 months (Visit 3-NB), occurrences of any medically assessed, RSV-associated LRTIs according to the case definitions	
From birth (Visit 1-NB) to 6 months (Visit 4-NB), occurrences of all-cause pneumonia	
From study intervention administration (Visit 1) to 6 months post-delivery (Contact 1), occurrence of RSV-associated medically attended RTIs (RSV-MA-RTIs)	
From birth (Visit 1-NB) to 12 months (Visit 5-NB), occurrences of RSV-associated hospitalizations according to the case definitions.	

CCI

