### Overall rationale for the current amendment:

This protocol has been amended to reflect the following:

- The Benefit/Risk assessment has been updated to clarify that:
  - The observed numerical imbalance in neonatal deaths is not an independent safety signal but a consequence of the validated signal of preterm births.
  - Based on the evaluation of the Study Day 43 post-birth interim analysis, GSK concluded that preterm birth is an identified risk for the pregnant women population, for the RSV Maternal vaccine candidate.
  - GSK has discontinued the work on this RSV Maternal vaccine candidate and is closing out all ongoing vaccine trials. GSK will continue to monitor and follow-up the immunized participants in the trials for the duration specified in the respective protocols.
- For vaccine efficacy (VE) related objectives, the sensitivity and supportive analyses will be only conducted for primary efficacy endpoints, but the sensitivity analysis using the negative binomial model has been removed.
- The following changes have been made to the secondary efficacy endpoints:
  - For efficacy endpoint from birth to 7 months and above, only the efficacy endpoints of “From birth (Visit 1-NB) to 12 months (Visit 5-NB), occurrences of severe medically assessed, RSV-associated LRTIs” and “From birth (Visit 1-NB) to 12 months (Visit 5-NB), occurrences of any medically assessed, RSV-associated LRTIs” will be kept, and the analyses will be conducted by using Kaplan-Meier curves from birth to 12 month, so that the VE changes across time can be observed.
  - “From birth (Visit 1-NB) to 6 months (Visit 4-NB), occurrences of any medically assessed, RSV-associated LRTIs by alternative case definitions” has been removed.
  - “From birth (Visit 1-NB) to 12 months (Visit 5-NB), time to the first occurrence of severe medically assessed, RSV-associated LRTIs according to the case definition” has been removed.
  - “From birth (Visit 1-NB) to 12 months (Visit 5-NB), time to the first occurrence of any medically assessed, RSV-associated LRTIs according to the case definition” has been removed.

- Secondary efficacy endpoints on infant participants will only be assessed in the Modified Full Efficacy set (FAS) and Secondary efficacy endpoints on maternal participants will only be assessed in the Exposed Set (ES).

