**9.4.4. Secondary endpoints**

**9.4.4.1. Efficacy (Amended 23 February 2023)**

The primary analysis of vaccine efficacy on secondary efficacy endpoints *in infants* will be based on the modified full analysis set for efficacy (modified FAS-E).

*The analysis of vaccine efficacy in maternal participants will be based on the Exposed set.*

Secondary Efficacy Endpoints	Statistical Analysis Methods
From birth (Visit 1-NB) to 6 months (Visit 4-NB), occurrences of RSV-associated hospitalizations according to the case definitions.	
CCI
 
From birth (Visit 1-NB) to 6 months (Visit 4-NB), occurrences of all-cause LRTIs.	
From birth (Visit 1-NB) to 6 months (Visit 4-NB), occurrences of all-cause LRTIs with hospitalization.	
From birth (Visit 1-NB) to 12 months (Visit 5-NB), occurrences of severe medically assessed, RSV-associated LRTIs according to the case definitions.	
From birth (Visit 1-NB) to 12 months (Visit 5-NB), occurrences of any medically assessed, RSV-associated LRTIs according to the case definitions.	

Secondary Efficacy Endpoints	Statistical Analysis Methods
From birth (Visit 1-NB) to 6 months (Visit 4-NB), occurrences of severe medically assessed, RSV-associated LRTIs according to the case definition, for RSV subtype A and RSV subtype B separately.	
From birth (Visit 1-NB) to 6 months (Visit 4-NB), occurrences of any medically assessed, RSV-associated LRTIs according to the case definition, for RSV subtype A and RSV subtype B separately.	
From birth (Visit 1-NB) to 4 months (Visit 3-NB), occurrences of severe medically assessed, RSV-associated LRTIs according to the case definition.	
From birth (Visit 1-NB) to 4 months (Visit 3-NB), occurrences of any medically assessed, RSV-associated LRTIs according to the case definitions.	
From birth (Visit 1-NB) to 6 months (Visit 4-NB), occurrences of all-cause pneumonia.	
From study intervention administration (Visit 1) to 6 months post-delivery (Contact 1), occurrence of RSV-associated medically attended RTIs (RSV-MA-RTIs).	
From birth (Visit 1-NB) to 12 months (Visit 5-NB), occurrences of RSV-associated hospitalizations according to the case definitions.	

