4. ANALYSIS SETS

4.1. Definition

For the purpose of the analysis the following analysis sets are defined.

Table 4 Maternal Participants

Analysis Set	Description
Enrolled	All maternal participants who completed the informed consent process and signed the informed consent form.
Exposed	All maternal participants who received the study intervention. The allocation in a group is done in function of the administered intervention.
Per Protocol - Immunogenicity	All maternal participants who received the study intervention to which they were randomised and have post-vaccination data minus participants with protocol deviations that lead to exclusion.
Solicited Safety – Stage A only	All maternal participants in the Exposed Set who have solicited safety data

Table 5 Infant participants

Analysis Set	Description
Exposed	Infants live-born to exposed maternal participants, whose parents/LARs completed the informed consent process and signed the informed consent form.
Per Protocol - Immunogenicity	All infant participants in the Exposed set minus those who (a) were born less than 4 weeks post- maternal participant vaccination and/ or (b) have protocol deviations that lead to exclusion.
Full Analysis - Efficacy	All infant participants in the Exposed set.
Modified Full Analysis - Efficacy	All infant participants in the Exposed set who were born after at least 4 weeks of vaccination.
Per Protocol - Efficacy	All infant participants in the Modified Full Analysis – Efficacy set minus those who have protocol deviations that lead to exclusion.

CONFIDENTIAL

212171 (RSV MAT-009)
Statistical Analysis Plan Amendment 5

Table 6 Overview of analysis sets and exclusion codes

Determined in mother or infant	Code	Description	Maternal analysis set				Infant analysis set				
			Enrolled	Exposed	Per Protocol - Immunogenicity	Solicited Safety	Exposed	Per Protocol - Immunogenicity	Modified Full Analysis - Efficacy	Full Analysis - Efficacy	Per Protocol - Efficacy
Mother	800, 800#	Fraudulent Data	Y	Y	Y	Y	Y	Y	Y	Y	Y
Mother	900, 900#	Invalid informed consent	Y	Y	Y	Y	Y	Y	Y	Y	Y
Mother	1030, 1030#	Study vaccine not administered		Y	Y	Y	Y	Y	Y	Y	Y
Mother	1040.Vx+*, 1040#	Administration of concomitant vaccine(s) forbidden in the protocol			Y			Y			Y
Mother	1050, 1050#	Randomisation failure			Y			Y			Y
Mother	1060, 1060#	Randomisation code was broken ^a			Y			Y			Y
Mother	1070, 1070#	Mother got vaccinated with the correct vaccine but incorrect volume			Y			Y			Y

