4.2. Criteria for eliminating data from Analysis Sets

4.2.1. Elimination from Exposed Set (ES)

4.2.2. Elimination from Modified Full Analysis Set for Efficacy (modified FAS-E)

4.2.2.1. Excluded Infants from Modified Full Analysis Set for Efficacy

An infant will be excluded from the modified FAS efficacy analysis under the following conditions:

Code	Condition under which the code is used	Visit (timepoints) where the code is applicable
800, 800#	Fraudulent data	All
900, 900#	Invalid informed consent	All
1030#	Study vaccine not administered	All
3100	Birth is less than 4 weeks post-vaccination	All

Carry forward elimination from mother to infant

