4.2.3. Elimination from Full Analysis Set for Efficacy (FAS-E)

4.2.3.1. Excluded Infants from Full Analysis Set for Efficacy

An infant will be excluded from the FAS efficacy analysis under the following conditions:

Code	Condition under which the code is used	Visit (timepoints) where the code is applicable
800, 800#	Fraudulent data	All
900, 900#	Invalid informed consent	All
1030#	Study vaccine not administered	All

Carry forward elimination from mother to infant

4.2.4. Elimination from Per protocol analysis set for Efficacy (PPS-E)**4.2.4.1. Excluded Infants from Per protocol analysis set for Efficacy (PPS-E)**

A participant will be excluded from the PPS efficacy analysis under following conditions:

Code	Condition under which the code is used	Visit (timepoints) where the code is applicable
800, 800#	Fraudulent data	All
900, 900#	Invalid informed consent	All
1030#	Study vaccine not administered	All
3100	Birth/Delivery is less than 4 weeks post-vaccination	All
1040#	Administration of concomitant vaccine(s) forbidden in the protocol	All
1050#	Randomisation failure	All
1060#	Randomisation code was broken	All
1070#	Mother got vaccinated with the correct vaccine but containing an incorrect volume	All
1070#	Vaccination not according to protocol (site of injection, route of administration, wrong replacement of study treatment administered)	All
1070#	Study treatment not prepared as per protocol (e.g. reconstitution)	All
1070#	Other deviations related to wrong study treatment/administration/dose	All
1070#	Study treatment administered while contraindicated	All
1080#	Vaccine temperature deviation	All
1090#	Expired vaccine administered	All
2010, 2010#	Protocol violation (inclusion/exclusion criteria)	All
2040*	Administration of any medication/product forbidden by the protocol (leading to elimination from PPS-E and PPS-I)	All
2240*	Administration of any medication/product forbidden by the protocol (leading to elimination from PPS-E)	All
2040*	Administration of any medication/product forbidden by the protocol (leading to elimination from PPS-E and PPS-I)	All
2050.Vx*	Intercurrent medical conditions/concomitant medications which are exclusionary as per protocol	All

Code	Condition under which the code is used	Visit (timepoints) where the code is applicable
2050#*	Maternal intercurrent medical conditions which are exclusionary as per protocol	All
2060#* 2060*	Concomitant infection related to the vaccine which may influence immune response	All

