5.2. Efficacy

5.2.1. Analysis of primary efficacy endpoints planned in the protocol

The primary analysis of vaccine efficacy (VE) will be based on the modified Full Analysis - Efficacy set for infants (modified FAS-E). A secondary analysis based on the Full Analysis – Efficacy set (FAS-E) and the Per Protocol - Efficacy set for infants will be performed to complement the modified FAS-E analysis.

Primary Efficacy Endpoints – Infant participants	Statistical Analysis Methods

From birth to 6 months, occurrences of medically assessed, RSV-associated severe LRTIs according to the case definitions.
 
OR
 
From birth to 6 months, occurrences of any medically assessed, RSV-associated LRTIs according to the case definitions.
	
CCI
 

CCI
 	

CCI

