5.4. Analysis of safety and reactogenicity

5.4.1. Analysis of safety and reactogenicity planned in the protocol

Safety analyses in **maternal participants** will include summaries by study group and age category (18-34, 35-39, ≥ 40 years of age; overall) of solicited administration site and systemic events (for stage A subjects), unsolicited AEs, MAEs, SAEs, MA-RTIs (RSV-associated MA-RTIs and all-cause MA-RTIs), AEs leading to study withdrawal, pregnancy outcomes and pregnancy related AESIs.

Safety analyses in **infant participants** will include summaries by study group, overall and gestational age at birth (≥ 37 weeks or < 37 weeks) of neonatal AESIs, MAEs, SAEs, AEs leading to study withdrawal, and the occurrence of RSV-associated RTIs, LRTIs, severe LRTIs, RSV-associated hospitalizations, all-cause RTI and all-cause LRTI.

Safety analyses for maternal participants and infants may also be reported by economic region (LMIC and HIC).

Analyses of solicited AEs will be performed on the Solicited Safety set (maternal participants only). Analyses of unsolicited AEs will be performed on the ES.

Primary Safety Endpoints – Infant Participants	Statistical Analysis Methods

Occurrence of SAEs, AEs leading to study termination and medically attended AEs from birth up to 6 months after birth
 
Occurrence of SAEs, AEs leading to study termination and medically attended AEs from birth up to 12 months after birth.
	
CCI

Secondary Safety Endpoints – Maternal Participants	Statistical Analysis Methods

Occurrence of solicited injection site and systemic events in Stage A participants during a 7-day follow-up period after vaccination (i.e. the day of vaccination and 6 subsequent days).
	
CCI

Occurrence of unsolicited adverse events (AEs) in all maternal participants during a 30-day follow-up period after vaccination (i.e. the day of vaccination and 29 subsequent days).
	

	CCI

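### Vaccine efficacy (VE) for the 11 secondary infant endpoints is planned only in infants born at least 4 weeks after vaccination, with no companion estimate in all exposed infants

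*SAP*

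**What the plan says.** **Secondary endpoints.** SAP 5.2.2 states that the main VE analysis of the secondary infant endpoints "will be based on the modified Full Analysis - Efficacy set (modified FAS-E"). Protocol 9.4.4.1 agrees: it "will be based on the modified full analysis set for efficacy (modified FAS-E"). Neither names another infant set. These sentences describe only the main analysis, so exclusivity rests on the protocol's rationale for Amendment 5: "Secondary efficacy endpoints on infant participants will only be assessed in the Modified Full Efficacy set (FAS"). The same rationale limits sensitivity and supportive VE analyses to the primary efficacy endpoints.

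**The two sets.** SAP Table 5 (4.1) defines FAS-E as "All infant participants in the Exposed set". Modified FAS-E (SAP 4.2.2.1) also applies code 3100, "Birth is less than 4 weeks post-vaccination". That code is absent from the FAS-E list in SAP 4.2.3.1, so the two sets differ by that code alone.

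**Primary endpoints.** For these, SAP 5.2.1 adds "A secondary analysis based on the Full Analysis – Efficacy set (FAS-E") and a per-protocol analysis.

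**Other cover.** SAP 5.4.1 plans infant summaries by group of "the occurrence of RSV-associated RTIs, LRTIs, severe LRTIs, RSV-associated hospitalizations, all-cause RTI and all-cause LRTI". SAEs and medically attended AEs to 6 and 12 months are primary safety endpoints, analysed on the Exposed set (protocol 9.4.3). RTI hospitalisations are reported as SAEs (protocol 8.3.1).

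**The concern.** Membership of modified FAS-E depends on when the infant was born, which is known only after randomisation. The sponsor concluded that preterm birth is an identified risk of this vaccine (protocol 2.3), so the vaccine may change who enters the set. The arms of modified FAS-E are then not fully protected by randomisation, and the estimate describes a narrower group than the infant participants named in the objectives.

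For the primary endpoints a reader can set the modified FAS-E and FAS-E results side by side. For the secondary endpoints no such pair is planned. What is at stake is interpretation: whether secondary VE would look the same in all exposed infants.

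**Working it through.** **1. Count of endpoints (SAP 5.2.2).** The table lists 12 secondary efficacy endpoints. One is maternal, which leaves 11 for infants:
- Six are variants of the primary outcomes: severe and any RSV LRTI to 4 months, to 12 months, and by subtype to 6 months.
- Five are other outcomes: RSV hospitalisation to 6 and to 12 months, and all-cause LRTI, all-cause LRTI with hospitalisation, and all-cause pneumonia to 6 months.

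FAS-E VE is planned for 2 of 2 primary efficacy endpoints and 0 of 11 secondary infant endpoints.

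**2. What the all-infant summaries cover.** The list in SAP 5.4.1 does not name subtype, pneumonia or all-cause LRTI with hospitalisation, so 4 of the 11 endpoints are unnamed. It states no VE and no 4-, 6- or 12-month window. The set appears to be the Exposed set, but SAP 5.4.1 states that set only for unsolicited AEs.

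**3. The preterm figure.** RR 1.38 (95% CI 1.08 to 1.75), p = 0.0090 (protocol 2.3).
- SE = ln(1.75/1.08)/(2 × 1.96) = 0.1231; z = ln(1.38)/0.1231 = 2.62; p = 0.0089, consistent with the stated value.
- With 3496 vaccine and 5235 − 3496 = 1739 placebo infants, this SE implies about 4.9% preterm on placebo and 4.9% × 1.38 ≈ 6.7% on vaccine.

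**4. Share excluded: an assumption.** The documents give no code 3100 counts. If 10-50% of preterm infants were born within 4 weeks of vaccination, about 0.5-2.4% of placebo infants would be excluded. That may be too low: vaccination is allowed at 34 weeks, so a birth at 37 weeks can be term and still excluded. I use 1-3% of placebo infants:
- placebo: 1739 × 0.01 = 17 to 1739 × 0.03 = 52;
- vaccine at RR 1.38: 3496 × 0.0138 = 48 to 3496 × 0.0414 = 145.

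**5. Possible difference in VE.** Let p = placebo share excluded, r = exclusion RR, k = relative RSV risk of excluded infants, e = VE in them, v = VE in the rest, and m = relative risk of infants born early only if vaccinated.

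VE(FAS-E) = 1 − [(1 − pr)(1 − v) + prk(1 − e)] / [(1 − pr) + p(r − 1)m + pk]

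VE(modified) = 1 − (1 − v)(1 − p) / [(1 − pr) + p(r − 1)m]

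Unfavourable case: r = 1.38, k = 2, e = 0, m = 1. For p = 1% and v = 50%:
- FAS-E: 1 − (0.9862 × 0.5 + 0.0276)/(0.9862 + 0.0038 + 0.02) = 1 − 0.5207/1.01 = 48.45%.
- Modified: 1 − 0.495/0.99 = 50.0%.

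| p | v | modified FAS-E | FAS-E | difference |
|---|---|---|---|---|
| 1% | 50% | 50.0% | 48.45% | 1.55 points |
| 3% | 50% | 50.0% | 45.43% | 4.57 points |
| 1% | 70% | 70.0% | 67.97% | 2.03 points |
| 3% | 70% | 70.0% | 64.04% | 5.96 points |

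A milder case (p = 2.4%, k = 1.5, e = v/2) gives 1.45 points at v = 50% and 1.85 at v = 70%. With r = 1, k = 1 and e = v the difference is zero.

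**6. Selection or a different population?** Setting r = 1 removes the arm imbalance. At p = 3%, k = 2, v = 50%:

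| VE in excluded infants | difference, r = 1 | difference, r = 1.38 | share left at r = 1 |
|---|---|---|---|
| 0% | 2.91 | 4.57 | 64% |
| 45% | 0.29 | 0.96 | 30% |
| 50% | 0.00 | 0.55 | 0% |

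The split depends on VE in the excluded infants, which is unknown.

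**7. Direction.** With p = 3%, r = 1.75 (the upper limit of the preterm CI), k = 0.5, m = 0.5 and e = v = 50%:
- Modified: 1 − 0.485/(0.9475 + 0.01125) = 49.4%.
- FAS-E: 1 − (0.47375 + 0.013125)/(0.9475 + 0.01125 + 0.015) = 50.0%.

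The sign can therefore reverse.

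**The case against.** **The restriction is deliberate and explained.** The protocol's list of main changes says secondary efficacy analyses were limited because enrolment stopped early. Modified FAS-E also has an immunological rationale in the amendment history: time for the maternal response and antibody transfer. Both points stand. This is a consistent design choice; the documents do not contradict each other, and dropping the companion analysis in Amendment 5 is not itself an error. But the stated reason concerns scope. It does not say that FAS-E is uninformative, and FAS-E was kept for the primary endpoints.

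**All-infant data will exist.** This stands in part. The occurrence summaries, and SAEs and medically attended AEs to 6 and 12 months, will capture many hospitalised or medically attended LRTI and pneumonia cases in all exposed infants. These are not VE, and they do not follow the efficacy case definitions and windows throughout. It would be wrong to infer that excluded infants go unreported.

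**The primary FAS-E result already shows any set effect.** This holds largely for the six RSV LRTI variants and much less for the other five endpoints.

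**VE is descriptive and the candidate is discontinued.** True (protocol 2.3 and 9.1, SAP section 8), and it keeps the priority low.

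**Redaction.** The methods cells in SAP 5.2.2 are blacked out, so the point rests on the visible text. The unredacted Amendment 5 wording makes a hidden FAS-E analysis unlikely.

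**Conclusion.** The point holds as a low-priority improvement. Secondary infant VE will describe only infants born at least 4 weeks after vaccination, and no all-infant VE is planned to set beside it. The gap lies mainly in RSV hospitalisation, all-cause LRTI, all-cause LRTI with hospitalisation, and pneumonia.

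Under the assumptions in steps 4 and 5 the difference is at most about 1.6-4.6 points at VE 50% and 2.0-6.0 at VE 70%. Those maxima need doubled risk and no protection in excluded infants together; milder inputs give under 2 points.

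A reader might infer that the planned secondary VE is biased in the vaccine's favour. The documents do not support that. They give no exclusion counts, no RSV risk in early-born infants and no VE in them. RR 1.38 concerns birth before 37 weeks, which is only a stand-in for birth within 4 weeks of vaccination. The sign can reverse, and how much of any difference is selection rather than a different population is unknown.

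**What to change.** - **SAP 5.2.2:** add a supportive VE analysis on FAS-E for the secondary infant efficacy endpoints, and keep modified FAS-E as the main set.
- **SAP section 8 and the clinical study report:** record the analysis as added after unblinding. Label it post hoc for the eight endpoints ending by 6 months, because the 6-month analysis of secondary efficacy is already done (SAP 7.1).
- **SAP 5.1.2:** in the planned infant disposition table, show code 3100 exclusions by arm. The count can be derived from the two sets, but an explicit line lets readers judge the exclusion directly.

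No protocol amendment is needed: protocol 9.4.1 sends changes to secondary objectives to the SAP and study report.

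The cost is a few extra tables on a set already defined and programmed for the primary endpoints. The amendment history shows that the companion analysis was planned for secondary endpoints before Amendment 5, so it can be restored rather than designed. The drawbacks are that the tables are post hoc and that VE may look slightly less favourable.
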